9.2 SAMPLE SIZE DETERMINATION

To determine the sample size, we averaged the gait parameters (across all age groups) along with pooled variance captured on the APDM inertial sensors for healthy subjects (53) and PD patients with gait disorder (54) and computed a reasonable sample size of 24 (which equates to a Cohen's $d=0.8$) with a power of 0.80 and level of significance of 0.05. Assuming a 20% attrition rate, we will attempt to recruit 30 patients.

Sample Size estimation

$(\alpha) = 0.05, Z_\alpha = 1.96$
 $(\beta) = 0.80$

$$n = \frac{2(Z_a + Z_{1-\beta})^2 \sigma^2}{\Delta^2}$$

Reference Gait values for healthy individuals using APDM sensors

Age Groups	n	mean	STD	Variance
		normalized speed		
20-29	41	1.14	0.12	0.0144
30-39	41	1.16	0.14	0.0196
40-49	42	1.14	0.16	0.0256
50-59	45	1.21	0.14	0.0196
60-69	51	1.13	0.12	0.0144
70-89	72	0.86	0.23	0.0529

Ages 50-89: Mean Velocity - 1.06

Calculated Pooled Variance for Ages 50-89- 0.03

Calculated Pooled Variance for All ages – 0.03

Gait Parameters for PD patients with gait disorder (FOG- & FOG +) using APDM sensors

Walking Measure		Single Task Mean \pm STD
Stride Length (m)	FoG-	1.06 \pm 0.15
	FoG+	0.92 \pm 0.22
Stride Velocity (m/s)	FoG-	0.99 \pm 0.18
	FoG+	0.86 \pm 0.21

Average age 68 STD 8.4 (FOG -)

Average Age 69 STD 7.9 (FOG+)

Mean Velocity – 0.925 (FOG- & FOG+)

de Souza Fortaleza AC, Mancini M, Carlson-Kuhta P, King LA, Nutt JG, Chagas EF, Freitas IFJ, Horak FB. Dual task interference on postural sway, postural transitions and gait in people with Parkinson's disease and freezing of gait. *Gait Posture*. 2017;56:76-81.

Effect Size 1.06-0.925 = .14

$N = 15.79 (.03)/ (.14)^2 = 24 + 20\% \text{ attrition} = \text{total study recruitment } 29 \text{ subjects.}$

Final Study N= 30 subjects

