7.2 PARTICIPANT DISCONTINUATION/WITHDRAWAL FROM THE STUDY

Participants are free to withdraw from participation in the study at any time upon request.

An investigator may discontinue or withdraw a participant from the study for the following reasons:

- Significant study intervention non-compliance
- If any clinical adverse event (AE) or other medical condition or situation occurs such that continued participation in the study would not be in the best interest of the participant

- Disease progression which requires discontinuation of the study intervention
- If the participant meets an exclusion criterion (either newly developed or not previously recognized) that precludes further study participation

The reason for participant discontinuation or withdrawal from the study will be recorded on the Case Report Form (eCRF). Subjects who sign the informed consent form, and receive the study intervention, and subsequently withdraw, or are withdrawn or discontinued from the study, will be replaced.

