9 STATISTICAL CONSIDERATIONS

9.1 STATISTICAL HYPOTHESES

Aim 1. Our preliminary study established that gait and rest tremor are important factors to determine whether patients benefit from 60Hz stimulation or high frequency stimulation (38). However, the degree to which stimulation parameters affect gait parameters is not well established. In Aim 1, we will test the *hypothesis* that certain gait parameters are differentially affected between 60Hz and high frequency STN-DBS at various electrode contact configurations. In addition, in our preliminary analysis, we observed a modest reduction in dopaminergic medications in patients on 60Hz stimulation (12). Hence, we will also test the *hypothesis* that for some patients, the addition of levodopa in combination with 60Hz stimulation produces a synergistic improvement in certain gait domains.

Aim 2. Our preliminary data suggested that there is a link between the patient's baseline motor symptomatology measured by the MDS-UPDRS III ratings and the best stimulation frequency (60 Hz or HFS) chosen for the patient based on intensive clinical evaluations, which remained unchanged for an average of 12 months. In Aim 2, we test the *hypothesis* that a subject's gait kinematics on 60Hz stimulation can be predicted with statistically significant accuracy using gait measurements on high frequency stimulation. In addition, we will test the *hypothesis* that the best stimulation frequency (60Hz or HFS stimulation), which yields improvement among various gait parameters, can be predicted using objective sensor data collected at baseline. We define baseline motor performance as the severity of motor symptoms in the levodopa OFF and ON state without stimulation. In the remainder of this proposal, for simplicity we refer to 60 Hz stimulation and high frequency stimulation (130-180Hz) as low frequency (LFS) and high frequency (HFS), respectively.

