9.4.2 ANALYSIS OF THE PRIMARY EFFICACY ENDPOINT(S)

Aim 1.1.

Using the analytical software of APDM, the SWAY and TUG algorithms included in the SAW test will calculate asymmetry and variability for: postural sway (RMS AP & ML planes), cadence (CN), gait cycle duration, gait speed (SN), swing, double support, elevation at midswing, foot strike angle, toe off angle, stance, step duration, stride length (LN), arm swing velocity, arm range of motion, turn angle, turn duration, and turn velocity. All data will be tested for normality with Shapiro-Wilk test. Linear mixed models with repeated measures (LMMRM) will be used to compare high and low frequency over all contact pairs in the levodopa-OFF state. Parameter estimation will be based on restricted maximum likelihood and the form of the covariance matrix will be chosen based on Akaike's Information Criteria and Schwarz' Bayesian Criterion. The Holm-Bonferroni method will be used to adjust for multiple comparisons for the 20 outcome measures.

Aim 1.2. To investigate levodopa's effects on the gait domains, we will include the data for levodopa-ON and add a binary variable for levodopa (on or off) to the LMMRM from Aim1.1.

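### The 0.80 power at N=24 in section 9.2 belongs to a healthy-versus-PD speed comparison at unadjusted 0.05; the power of the Aim 1.1 test (60 Hz against high frequency, within patients, under Holm) is not stated and cannot be derived

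*Combined protocol and SAP*

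**What the plan says.** **Section 9.2 (sample size).** The formula is n = 2(Zα + Z1−β)²σ²/Δ², "with a power of 0.80 and level of significance of 0.05". The inputs are:

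- Effect: "Effect Size 1.06-0.925 = .14". The 1.06 is the mean speed of healthy adults aged 50-89. The 0.925 is the mean stride velocity of PD patients with and without freezing.
- Variance: "Calculated Pooled Variance for Ages 50-89- 0.03". The table behind it is the healthy reference table, in a column headed "normalized speed". The same 0.03 is given for all ages.
- Recruitment: "Assuming a 20% attrition rate, we will attempt to recruit 30 patients".

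**Section 9.1 (Aim 1 hypothesis).** The claim to be tested is that "certain gait parameters are differentially affected between 60Hz and high frequency STN-DBS at various electrode contact configurations".

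**Section 9.4.2 (Aim 1.1 analysis).** A repeated-measures linear mixed model compares high with low frequency over all contact pairs in the levodopa-OFF state. Holm-Bonferroni is applied for a stated 20 outcome measures. Section 4.1 gives the data structure: eight trials per patient, four contact pairs at each of two frequencies.

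**The concern.** A reader of section 9.2 will take 0.80 to be the chance that Aim 1.1 detects the effect it is looking for. Three inputs belong to a different comparison:

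1. **Contrast.** The 0.14 separates healthy people from patients. The trial enrols no healthy group, and no passage gives an expected difference between 60 Hz and high frequency. Section 9.1 itself says that how far stimulation parameters affect gait is not well established.
2. **Variance.** The 0.03 is a spread between healthy people. The planned test depends on the SD of each patient's own difference between frequencies, and neither that SD nor a within-patient correlation is given.
3. **Alpha.** The 0.05 suits a single outcome. Under Holm with 20 outcomes, the smallest p-value is compared with 0.0025.

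At stake is how the trial's sensitivity is described. Aim 1.1 is a primary aim with formal multiplicity control, and section 2.1 says the study is to prepare a randomized trial. A planned power of 0.80 that refers to another comparison would mislead whoever uses the result.

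**Working it through.** **Step 1. Reproduce the plan's figure.** From section 9.2: constant 15.79, σ² = 0.03, Δ = 0.14.

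15.79 × 0.03 / 0.14² = 0.4737 / 0.0196 = 24.17, stated as 24.

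d = 0.14/√0.03 = 0.81, consistent with the stated 0.8. Allowing for 20% loss, 24/0.8 = 30 (and 24 × 1.2 = 28.8, which explains the 29 also shown). The arithmetic holds. Read as a comparison of two independent groups, 24 is the size of each group, with power 0.80.

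**Step 2. Trace the variance.** Pooling the healthy table with n−1 weights gives 0.0324 for ages 50-89 and 0.0271 for all ages. Both round to 0.03. The PD table in the same section has stride-velocity SDs of 0.18 and 0.21, so a mean variance of (0.0324 + 0.0441)/2 = 0.038, which is not the figure used.

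**Step 3. Set up the planned contrast.** Simplify the mixed model to one value per patient per frequency, averaged over contact pairs. With within-patient correlation ρ:

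- variance of the difference = 2σ²(1 − ρ)
- dz = Δ/√(2σ²(1 − ρ))
- power from the noncentral t with n − 1 degrees of freedom and noncentrality dz√n, two-sided

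At ρ = 0 the variance is 2σ², so the section 9.2 formula is also the normal-approximation number of pairs for a paired test with uncorrelated measurements.

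**Step 4. Illustrative power.** Assumptions, none supplied by the documents for this contrast: the true frequency effect is 0.14, σ² = 0.03, and ρ ranges over 0 to 0.8.

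| ρ | dz | n=24, α=0.05 | n=24, α=0.0025 | n=30, α=0.05 | n=30, α=0.0025 |
|---|---|---|---|---|---|
| 0 | 0.572 | 0.76 | 0.31 | 0.86 | 0.45 |
| 0.5 | 0.808 | 0.97 | 0.71 | 0.99 | 0.85 |
| 0.8 | 1.278 | >0.99 | 0.995 | >0.99 | >0.99 |

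If the true effect were half as large (0.07), power with 24 completers at 0.0025 would be 0.11 at ρ = 0.5 and 0.42 at ρ = 0.8. The answer depends on quantities that the plan does not state.

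**Step 5. What can be said without assuming an effect, variance or correlation.** Solve for the dz that gives 80% power:

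| Completers | α = 0.05 | α = 0.0025 |
|---|---|---|
| 24 | 0.60 | 0.88 |
| 30 | 0.53 | 0.77 |

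Both counts are shown because section 9.2 allows for 20% loss, while section 7.2 says that subjects who receive the intervention and "subsequently withdraw, or are withdrawn or discontinued from the study, will be replaced".

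**Step 6. The Holm count.** Counting the section 9.4.2 list, with the two sway planes taken separately, gives 18 named measures against 20 stated. With 18, the first step is 0.05/18 = 0.0028 and the detectable dz with 24 completers is 0.87 instead of 0.88, so the discrepancy hardly moves the result.

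**The case against.** The strongest defence is that the 24 is serviceable and perhaps cautious. Because 2σ² is the paired variance at ρ = 0, 24 can be read as a number of patients in a within-patient test, and any positive correlation raises power for a given σ. At 0.05 the illustration gives 0.97 at ρ = 0.5. The 0.0025 threshold is Holm's strictest step and later steps are easier. The missing frequency effect is openly acknowledged, and what a null result rules out will be read from its confidence interval rather than from planned power. All of this stands, and it limits the point to what section 9.2 may claim. It does not supply a frequency effect, a within-patient SD or an adjusted alpha, so it does not make 0.80 the power of Aim 1.1.

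Several stronger readings are tempting, and the documents do not support them:

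- *The trial is underpowered.* Pairing and Holm pull in opposite directions and the true effect is unknown.
- *The arithmetic is wrong.* It reproduces.
- *The detectable effect can be restated as a gait speed using √0.03.* That would reuse the healthy-subject variance criticised here, when section 9.2 also reports PD SDs of 0.18 and 0.21.
- *Familywise error is inflated.* Section 9.4.2 says that "the SWAY and TUG algorithms included in the SAW test will calculate asymmetry and variability for" the listed measures, which might suggest a larger set of tests, but nowhere does it say that more than 20 are tested with a divisor of 20.
- *Attrition and replacement contradict each other.* Section 7.2 replaces only those who withdraw after receiving the intervention, so some loss is still compatible with it.

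**Conclusion.** The point holds as a mismatch between the sample-size basis and the planned analysis. The 0.80 in section 9.2 is not the power of the Aim 1.1 test: effect, variance and alpha all come from a different setting. The power of the planned test is unknown and could be above or below 0.80. At the first Holm step with 24 completers, the illustration runs from 0.31 to 0.995 as ρ goes from 0 to 0.8, and that range assumes a true effect of 0.14 and a variance of 0.03. The detectable dz values rest only on a paired t simplification, two-sided testing, 80% power and the number of completers. They describe the overall frequency contrast and not frequency-by-contact effects, which the Aim 1 hypothesis also touches. No change to the size or design of the trial follows.

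**What to change.** Keep N=30, the endpoints and the mixed model. In section 9.2, keep the calculation as the historical basis for N, and stop presenting 0.80 as the power of Aim 1.1. Add beside it:

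> For the overall paired 60 Hz-HFS contrast (one value per patient per frequency, averaged over contact pairs; two-sided, 80% power), the detectable standardised within-patient difference dz is 0.60 at 0.05 and 0.88 at the Holm first step of 0.0025 with 24 completers, or 0.53 and 0.77 with 30. Later Holm steps are less strict. Averaging over contact pairs may reduce the raw difference that corresponds to a given dz, but not dz itself. These figures do not cover frequency-by-contact effects.

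Do not add speed equivalents based on √0.03 or familywise error figures for larger outcome sets. As a minor consistency point, make the Holm count in section 9.4.2 match the measures listed (18 named, 20 stated).

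Cost: wording only, with no added patients and no change to the analysis. The downside is that the stated figure becomes less favourable than a plain 0.80.

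### Section 9.2's inputs contradict its own tables and text, so d = 0.8 and 80% power at n = 24 are not supported as written

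*Combined protocol and SAP*

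**What the plan says.** Section 9.2 (Sample Size Determination) describes its method in a paragraph and then prints the calculation.

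- The paragraph says "we averaged the gait parameters (across all age groups) along with pooled variance captured on the APDM inertial sensors", for healthy subjects and for PD patients with gait disorder. It reports a sample size of 24, equated to Cohen's d = 0.8, "with a power of 0.80 and level of significance of 0.05".
- The healthy reference table gives n, mean and SD for six age bands. The calculation takes "Ages 50-89: Mean Velocity - 1.06" and "Calculated Pooled Variance for Ages 50-89- 0.03". A pooled variance of 0.03 is also printed for all ages.
- The PD table gives stride velocity 0.99 ± 0.18 (FoG-) and 0.86 ± 0.21 (FoG+), with a mean of 0.925.
- The difference is printed as "Effect Size 1.06-0.925 = .14".
- The last step is 15.79 × 0.03 / 0.14² = 24, raised for 20% attrition to 29, with a final figure of 30.

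Section 9.4.2 (Aim 1.1) compares high and low frequency over all contact pairs in the levodopa-OFF state with a repeated-measures linear mixed model. Holm-Bonferroni adjustment covers 20 outcome measures.

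**The concern.** The paragraph and the calculation describe different things. The paragraph names all age groups and a variance drawn from both healthy and PD subjects. The calculation uses ages 50-89, and no PD variance is shown entering it. Within the calculation, the healthy mean does not match its table and the difference is rounded up before it is squared.

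Required n varies with the inverse square of the difference, so a shift of 0.02 to 0.03 in a difference of about 0.14 changes it materially. At stake are three figures that a reader would take as the justification for enrolment: d = 0.8, n = 24 and power 0.80. If they cannot be traced to the plan's own tables, a null result on a gait parameter cannot be read against a known detectable effect.

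**Working it through.** **Inputs (Section 9.2).** Healthy rows for ages 50-89: "50-59 45 1.21 0.14 0.0196" and "60-69 51 1.13 0.12 0.0144" (age band, n, mean, SD, variance); for ages 70-89, n 72, mean 0.86, SD 0.23, variance 0.0529. PD mean 0.925, the unweighted mean of 0.99 and 0.86. Two-sided alpha 0.05 is implied by Z = 1.96; power is 0.80.

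**Formula.** n = 2(Zα + Zβ)²σ²/Δ². The exact constant is 2(1.960 + 0.8416)² = 15.70. The plan's 15.79 is 2(1.96 + 0.85)². Power at 24 is Φ(Δ/√(2σ²/24) − 1.96).

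**The plan's figure.** 15.79 × 0.03 / 0.14² = 24.2, and d = 0.14/√0.03 = 0.81. So 24 reproduces from the inputs as entered; the question is whether those inputs hold.

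**Healthy mean, ages 50-89.**
- Weighted by n: (45×1.21 + 51×1.13 + 72×0.86)/168 = 174.00/168 = 1.036.
- Unweighted: (1.21 + 1.13 + 0.86)/3 = 1.067, which rounds to 1.07. It gives 1.06 only by truncation.

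**Difference.** 1.06 − 0.925 = 0.135. With variance 0.03, n = 15.70 × 0.03 / 0.135² = 25.8, so 26; power at 24 is 77% and d = 0.78.

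**Variance.**
- Ages 50-89, pooled by degrees of freedom: (44×0.0196 + 50×0.0144 + 71×0.0529)/165 = 0.0324. Simple average: 0.0290. Either rounds to 0.03.
- All ages, pooled by degrees of freedom: 0.0271. Simple average: 0.0244, which would round to 0.02. The printed all-ages 0.03 therefore points to size-weighted pooling.
- PD: (0.18² + 0.21²)/2 = 0.0383.
- Healthy 50-89 (pooled) and PD averaged: (0.0324 + 0.0383)/2 = 0.0353.

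**Results under each reading.**

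| Healthy mean | Δ | Variance | n | Power at 24 |
|---|---|---|---|---|
| 50-89, n-weighted | 0.111 | 0.03 | 39 | 60% |
| | | 0.0324 | 42 | 57% |
| | | 0.0353 (PD averaged in) | 46 | 53% |
| | | 0.0383 (PD) | 49 | 50% |
| 50-89, unweighted | 0.142 | 0.0290 | 23 | 82% |
| | | 0.03 | 24 | 81% |
| | | 0.0324 | 26 | 78% |
| | | 0.0353 (PD averaged in) | 28 | 74% |
| All ages, n-weighted (1.083) | 0.158 | 0.0271 | 18 | 91% |
| | | 0.03 | 19 | 88% |
| | | 0.0353 (PD averaged in) | 23 | 83% |
| | | 0.0383 (PD) | 25 | 80% |

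**What 24 completers can detect within patient.** By a two-sided paired t-test with 80% power, the detectable difference, in units of the SD of within-patient differences, is 0.60 at alpha 0.05. At the first Holm step, 0.05/20 = 0.0025, it is 0.88.

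**The case against.** The strongest reply is that 24 can be recovered. Averaging the three age rows without weights, as the plan did for the PD mean, gives Δ = 0.142. That rounds to the printed 0.14 and yields 81-82% power with variance 0.03 or 0.0290. The all-ages basis named in the text gives about 80-91%. On this view the discrepancies are rounding and loose wording, and 30 are recruited in any case.

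Much of this stands. A reader might infer that no consistent reading of the 50-89 inputs gives 80% power, or that the trial has only 50-60% power. The documents support neither: simple averaging of both mean and variance does reach 80%, and the low figures require n-weighting of the mean, which the plan does not state. A reader might also infer that "normalized speed" in the healthy table is on a different scale from the PD velocities. That is not established: the height normalisation in Section 9.4.1 leaves speed in m/s, and the documents do not show how the reference source normalised.

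The reply does not make the section correct. The favourable 50-89 reading is not the one printed, since it needs a mean of 1.067. It also sits poorly with the all-ages variance, which reaches 0.03 only by size-weighted pooling; with the pooled 50-89 variance of 0.0324 it gives 78%. The favourable all-ages reading uses a mean that the calculation did not use. The 30 recruited are there to cover attrition, so they are not spare sample size.

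**Conclusion.** Section 9.2 is internally inconsistent, and d = 0.8 with 80% power at 24 is not supported as written. The healthy mean matches neither average of its rows, 0.135 is entered as 0.14, and the stated age range and variance source differ from those used. The plan's own subtraction, left unrounded, needs 26 and gives 77% at 24. Beyond that, power runs from about 50% to 91% according to choices of age range, weighting and variance that the plan leaves open. The loss to 50-60% is conditional on n-weighting the 50-89 mean.

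All these powers use the plan's normal approximation with 24 per group in two independent groups. They test its arithmetic only. None is the power of Aim 1.1, a within-patient comparison for which the plan gives neither a within-patient SD nor a correlation.

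**What to change.** Preferred: withdraw the healthy-minus-PD derivation with its d = 0.8 and 80% power. State instead that 24 completers give 80% power, by a paired t-test approximation to the Aim 1.1 mixed model, to detect a standardised within-patient difference of about 0.60 at two-sided alpha 0.05, or about 0.88 at the first Holm step of 0.0025.

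If the derivation is kept: use one age range, one weighting for both mean and variance, and the healthy-plus-PD variance that the text names. Carry full precision to the last step, restate d and power for 24, and say that the result is not the power of the Aim 1.1 analysis.

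Cost: protocol wording only, with no extra patients, visits or data. The stated figure may become less favourable.

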9.3 POPULATIONS FOR ANALYSES

Not applicable

9.4 STATISTICAL ANALYSES

9.4.1 GENERAL APPROACH

We will perform descriptive statistics—i.e., mean (standard deviation) on all demographic, LED, MDS-UPDRS III (Total score), baseline DBS parameters and gait kinematic parameters. In order to eliminate body height as a confounder, we will normalize (N), according to gender, the following parameters: speed (S), stride length (L), cadence (C) according to Schwesig et al.(55).

$$D = \sqrt{\text{body height}/\text{mean body height}}$$

$$S_N = S / D^2$$

$$L_N = L / D^2$$

$$C_N = C \times D^2$$

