1 PROTOCOL SUMMARY

1.1 SYNOPSIS

Title: Computational Modeling of 60 Hz Subthalamic Nucleus Deep Brain Stimulation for Gait Disorder in Parkinson's disease

Study Description: The goal of this research is to further our understanding and application of deep brain stimulation in Parkinson's patients with gait disorder.

We will assess the degree to which stimulation parameters affect gait parameters. We will test the hypothesis that the addition of levodopa in combination with stimulation produces a synergistic improvement in certain gait domains. In addition, we test the hypothesis that a subject's gait on stimulation can be predicted with statistically significant accuracy using gait measurements on high frequency stimulation. Finally, we will test the hypothesis that the best stimulation frequency, which yields improvement among various gait parameters, can be predicted using objective sensor data collected at baseline

Objectives:

Aim 1: To determine the impact of 60Hz subthalamic deep brain stimulation on gait kinematics using wearable sensors

- Aim 1.1: To determine whether 60Hz STN-DBS elicits a differential response in gait kinematics compared to high frequency
- Aim 1.2: To determine the influence of 60Hz STN-DBS and levodopa on gait kinematics

Aim 2: To develop machine learning models to predict optimal subthalamic deep brain stimulation frequency based on wearable sensor profiles of baseline Parkinson's motor symptoms

- Aim 2.1: To develop machine learning models to predict gait response to 60Hz stimulation without additional testing
- Aim 2.2: To develop machine learning models to predict best stimulation frequency (60Hz vs. high frequency).

Endpoints:

Primary Endpoints:

Gait parameters:

- Postural sway – root mean square (RMS) sway in antero-posterior (AP) and medio-lateral (ML) planes;
- Gait – cycle duration (seconds), speed (m/s), stance (%), swing (%), heel strike angle (degrees), toe off angle (degrees), stride length (cm), cadence (steps/min), step duration (seconds), elevation at midswing (cm) (foot clearance), double support (%), arm swing velocity (deg/s), and range of motion (degrees);

- Circumduction – turn angle (degrees), turn duration (seconds), and turn velocity (deg/s).

Machine learning models to: 1) predict gait kinematics on 60Hz STN-DBS; 2) predict best stimulation frequency using wearable sensor data collected at baseline.

Secondary Endpoints:

Tremor (rest, kinetic, postural)

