Aim 2.2. Similar to Aim 2.1, in this sub-Aim we conduct regression analysis to predict gait parameters. However, in this sub-Aim, gait parameters are predicted on low and high frequency in the context of ON and OFF medication conditions using baseline bradykinesia, tremor, and gait sensor measurements, plus MDS-UPDRS III rigidity and axial sub scores. Patient and disease characteristics will be used as regressors. Again, models will be based on RF classifier, where other modeling techniques, such as neural networks, will be used as benchmarks. The best performing parameters identified in Aim 2.1 will be used to guide the model building in this sub-Aim. Also, aforementioned performance enhancing techniques will be used, if possible, and confidence intervals will be generated using bootstrapping. These models will be able to predict the best stimulation frequency and contact pairs for the patient immediately after baseline evaluations and provide a confidence level. Similar to Aim 2.1, we will

develop these models with and without accounting for PD medications to further quantify their impact and provide additional options for patients.

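### The three height-normalisation formulas in section 9.4.1 are mutually inconsistent, so normalised speed, stride length and cadence cannot all be free of body height

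*Combined protocol and SAP*

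**What the plan says.** Section 9.4.1 gives the purpose and scope of the step: "In order to eliminate body height as a confounder, we will normalize (N), according to gender, the following parameters: speed (S), stride length (L", followed by cadence. It defines D as the square root of body height over mean body height and then gives

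- S_N = S / D²
- L_N = L / D²
- C_N = C × D²

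The formulas are attributed to a cited study of inertial-sensor reference gait data in healthy subjects. The section gives no derivation and no value for mean body height. It does not say whether that mean comes from the sample or from an external reference.

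All three parameters are primary endpoints. Section 1.1 lists speed in m/s and then "stride length (cm), cadence (steps/min), step duration (seconds". Section 9.4.2 carries the normalised versions into the Aim 1.1 outcome list, for example "cadence (CN), gait cycle duration, gait speed (SN), swing, double support", with stride length marked L_N later in the same list. The Aim 1.1 mixed models "will be used to compare high and low frequency over all contact pairs in the levodopa-OFF state". For Aim 2.2 the same section says that "gait parameters are predicted on low and high frequency in the context of ON and OFF medication conditions using baseline bradykinesia, tremor, and gait sensor" data, without saying whether the gait values are normalised. For Aim 2.1 it refers to raw Phase II data.

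**The concern.** Speed, stride length and cadence from one walk are tied together: any two determine the third. A normalisation that removes height from all three must respect that tie, and the stated formulas do not. A programmer who follows the plan exactly would report three primary outcomes from the same walk that disagree with each other for every patient not of mean height. At least one of them would still depend on height, or would depend on it because of the adjustment. The stated purpose of the step would not be met wherever patients are compared with one another.

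**Working it through.** **Inputs.** The formulas for D, S_N, L_N and C_N are from section 9.4.1. The units are from section 1.1. Example values are from the section 9.2 table for Parkinson's patients with gait disorder: mean stride velocity 0.925 m/s, as stated there, and mean stride length (1.06 + 0.92)/2 = 0.99 m. The plan attaches no numerical result to the normalisation, so there is no figure of its own to reproduce.

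**Step 1: the identity.** A stride is two steps. Cadence in steps/min divided by 120 is therefore strides per second, and

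S (m/s) = L (m) × C (steps/min) / 120.

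With the example values, C = 0.925 × 120 / 0.99 = 112.1 steps/min.

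**Step 2: substitute the plan's formulas.**

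L_N × C_N / 120 = (L/D²)(C × D²)/120 = L × C/120 = S.

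The plan sets S_N = S/D². Hence S_N / (L_N × C_N / 120) = 1/D² = mean height / height.

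| Height / mean height | S_N ÷ (L_N × C_N / 120) |
|---|---|
| 0.85 | 1.176 |
| 0.90 | 1.111 |
| 0.95 | 1.053 |
| 1.00 | 1.000 |
| 1.05 | 0.952 |
| 1.10 | 0.909 |
| 1.15 | 0.870 |

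With the example values at height ratio 0.90: S_N = 0.925/0.90 = 1.028 m/s, L_N = 0.99/0.90 = 1.100 m, C_N = 112.1 × 0.90 = 100.9, and 1.100 × 100.9/120 = 0.925. At ratio 1.10: S_N = 0.841, L_N = 0.900, C_N = 123.3, and 0.900 × 123.3/120 = 0.925.

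**Step 3: can any true scaling rescue the set?** Let raw L vary as height^a and raw C as height^b, so that raw S varies as height^(a+b). The height exponents left after normalisation are a − 1 for L_N, b + 1 for C_N and a + b − 1 for S_N. Then

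(a + b − 1) − (a − 1) − (b + 1) = −1 for every a and b.

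The three remainders therefore cannot all be zero.

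| Assumed height-free | Left over | Size at 10% below / above mean height |
|---|---|---|
| L_N and C_N | S_N ~ height^−1 | +11% / −9% |
| L_N and S_N | C_N ~ height^+1 | −10% / +10% |
| S_N and C_N | L_N ~ height^+1 (raw L ~ height²) | −10% / +10% |

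If stride length is proportional to height (a = 1), the remainders are b for S_N and b + 1 for C_N, which cannot both be zero. As an illustration under a scaling that is not in the documents (L ~ height, C ~ height^−0.5, S ~ height^0.5), L_N is height-free. S_N is then off by +5.4% / −4.7% and C_N by −5.1% / +4.9%.

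**Step 4: effect on the Aim 1.1 contrast.** Height is fixed within a patient, so normalisation multiplies that patient's low-minus-high frequency difference by one positive constant. An illustrative simulation used 24 paired patients, an assumed mean difference of 0.06 with SD 0.10, a height coefficient of variation of 3% to 6%, and 4,000 replicates per setting. Power was 0.80 to 0.81 with and without the rescaling, and the two t statistics correlated above 0.998.

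**Step 5: a consistent set exists.** With the plan's own D, take S/D, L/D² and C × D. Then (L/D²)(C × D)/120 = (L × C/120)/D = S/D, as required.

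**The case against.** The strongest reply is that the algebra is right but changes little. The primary comparison is within patients, so height cannot confound it or reverse the sign of any patient's difference, and step 4 shows almost no effect on the test. That stands. A reader might infer from the stated purpose that the frequency comparison is confounded by height. The repeated-measures design rules this out.

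Three other inferences are tempting and also go too far.

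- **Aim 2 is contaminated.** The S_N, L_N and C_N labels appear only under Aim 1.1. Aim 2.1 refers to raw data and Aim 2.2 is silent. Even if normalised values were used, a patient's 60 Hz and high-frequency values share the same multiplier, so which frequency is better on a given parameter would not change.
- **The speed and cadence formulas are the wrong ones.** D is defined as a square root but used only squared, which would fit a slip in the exponents. The documents cannot confirm that, and the cited source is not available here. Singling out speed and cadence also needs stride length to be proportional to height. Without that assumption, only the set of three is shown to be contradictory.
- **The gap in S_N between a short and a tall patient walking at equal raw speed can be set against the 0.14 m/s effect in section 9.2.** Any height normalisation must separate two such patients, so the gap does not measure error. The plan also normalises by gender against a mean height that it does not give, and the 0.14 m/s is a difference between healthy people and patients.

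None of this repairs the formulas, and no other section changes them.

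**Conclusion.** The inconsistency is certain on the formulas as printed; it needs only the two-steps-per-stride identity. Its size is the ratio of mean height to height: 11% at 10% below mean height and 9% at 10% above. At least one of the three normalised primary outcomes keeps or gains a height effect. If stride length is proportional to height, normalised speed and cadence cannot both be height-free. Which formula is wrong cannot be settled from the documents.

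The practical weight lies in between-patient uses: the descriptive statistics of section 9.4.1 and the age, gender and disease-duration subgroups of section 9.4.7. It extends to Aim 2 only if normalised values are used there. For the Aim 1.1 contrast the effect is small, though the near-identical power rests on the assumed differences and height spread in step 4. The point is worth correcting because following the plan as written yields incompatible values for three primary outcomes and misses the stated aim of the step.

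**What to change.** 1. Check the exponents on the original page and against the cited source. Replace the formulas with a set that satisfies S_N = L_N × C_N / 120, for example S/D, L/D² and C × D if the source supports it, and use that set for descriptive and other between-patient summaries.
2. State which mean body height is used: the sex-specific sample mean or an external reference.
3. For the within-patient contrasts of Aim 1, analyse unnormalised speed, stride length and cadence. Height is constant within a patient, so nothing is lost, and the estimates stay in the units of the endpoint list. The number of outcomes in the Holm-Bonferroni family does not change.
4. State for Aim 2.1 and Aim 2.2 whether the gait predictors and targets are raw or normalised.

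The cost is an edit to the SAP and the analysis code. Height is already collected at visit 1, so no new data are needed.
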